- 9 Analysis of samples can be completed at a local, qualified laboratory. The investigative site should notify the study team if the local laboratory cannot test all the analytes listed in Table 5. If the total thyroxine (Total T4), free T4, uric acid, gamma glutamyl transferase, inorganic phosphorous, very low-density lipoprotein, or globulin parameters are not available through the local laboratory, and alternative arrangements cannot be made, testing of these analytes may be omitted provided other subject-assessments of thyroid function (ie, thyroid-stimulating hormone), lipid metabolism (ie, triglycerides, low-density lipoprotein, high-density lipoprotein, and total cholesterol), and protein metabolism (ie, total protein and albumin) are available and confirmed to be stable as per the Investigator. Alternative arrangements to test the listed analytes are to be made if the Investigator, Medical Monitor, or sponsor determines that they have the potential to impact subject safety. In the event the local laboratory is unable to test any other analytes, they may be omitted in exceptional circumstances after consultation with the sponsor. Such exceptions will not be applied to any of the key safety analytes (see Section 7.2.6).
- 10 If urinalysis results are abnormal, then a microscopic evaluation will be completed.
- 11 Pregnancy testing will be performed monthly for females of child-bearing potential. A urine pregnancy test will be performed only when a serum pregnancy test is not obtained.
- 12 Age-appropriate versions of the FOP-PFQ and PROMIS Global Health Scale will be used.
- 13 CAJIS assessment may be performed remotely or by videoconferencing.
- 14 Baseline for low-dose WBCT scan, excluding head, will be at Part C Screening (ie, when the subject provides informed consent/assent for Study PVO-1A-202 Part C). The low-dose WBCT scans, excluding head, will only be performed during annual visits (not at the 6-month visit).
- 15 Blood samples for PK assessment of non-flare-up dosing will be collected at the first 3-month safety assessment at pre-dose and 3, 6, 10, and 24 hours post-dose; if samples cannot be or were not obtained at the 3-month safety assessment, or if a subject is on flare-up-based treatment, then the PK blood sample for non-flare-up-based treatment can be obtained during any subsequent 3-month safety visit.

AE = adverse event(s), AP = anterior/posterior, CAJIS = Cumulative Analogue Joint Involvement Scale for FOP, C-SSRS = Columbia Suicide Severity Rating Scale, EOS = end of study, EOT = end of treatment, FOP-PFQ = Fibrodysplasia Ossificans Progressiva physical function questionnaire, P/A = posterior/anterior, PK = pharmacokinetic, PROMIS = Patient Reported Outcomes Measurement Information System, WBCT = whole body computed tomography.

**Table 3. Schedule of Assessments for Flare-up-based Treatment (Subjects with a Flare-Up)**

Assessment/Procedure	Flare-Up Cycle Safety Day 1 	FLARE-UP CYCLE SAFETY ASSESSMENTS Remote Visits  (±5 days)		
		Every 12 Weeks 		
Vital signs and body weight	X	X		
Hematology 	X	X		
Biochemistry (includes lipids) 	X	X		
Urinalysis 	X	X		
C-SSRS (age appropriate)	X	X		
Pregnancy testing 	X	Every 4 weeks		
Study drug dispensing		As needed from Cycle Day 1 to end of treatment of last flare-up cycle 		
Study drug treatment		Continuous from Cycle Day 1 to end of treatment of last flare-up cycle 		
Dispense/review subject diary		Dispense diary as needed and review at every subject contact		
Flare-up(s) status and end date confirmation 	X	At every subject contact		
Prior/concomitant medications		At every subject contact		
Adverse events		At every subject contact		
FLARE-UP TREATMENT AND PHARMACOKINETICS				
Treatment/Assessment	Flare-Up Day 1 	High Dose Treatment	Low Dose Treatment	
Flare-up (first flare-up or restart for intercurrent flare-up) 	X	Week 1 to 4 (4 weeks)	Week 4 to 12 (8 weeks)	4-Week Extension (if applicable)
Pharmacokinetic blood sample		X 	X 	
Telephone contact 			End of Week 12	End of each 4-week extension

-  All visit windows are ±5 days, except the End of Flare-Up Cycle Safety Assessments of the first flare-up, which is -5 days because a blood draw is required for pharmacokinetic analysis.
-  Remote visits will be performed at the subject’s home by qualified study personnel or at a local medical facility, unless the Investigator deems that a site visit is necessary. Remote visits during treatment extension, if applicable, will occur every 12 weeks until all the flare-ups within a cycle have resolved and treatment has been completed.
-  A Flare-up Cycle will include the first flare-up and any subsequent intercurrent flare-ups or traumatic events during the same dosing period. Flare-Up Cycle Safety Day 1 is defined as the first day that study drug is administered for the first flare-up or traumatic event upon confirmation by the Investigator. Flare-up cycle safety assessments will be performed on Flare-up Cycle Safety Day 1 and then every 12 weeks thereafter until treatment of the last flare-up or traumatic event within a Flare-up Cycle is completed. If treatment of the last flare-up or traumatic event in a cycle resolves within 4 weeks of the last flare-up cycle safety assessment, then another flare-up cycle safety visit does not need to be performed. Once all flare-ups in a cycle have resolved and flare-up-based treatment has been completed, subjects will resume non-flare-up-based treatment with 5 mg palovarotene once daily (weight-adjusted doses for skeletally immature subjects). It is possible that

- subjects may experience more than one Flare-up Cycle during Part C of the study. Note that the Flare-up Cycle assessments will also be applicable to any treated high-risk traumatic event likely to lead to a flare-up.
- 4 Flare-up-based treatment can begin immediately after the Investigator confirms the presence of a flare-up and prior to availability of safety laboratory results, unless the Investigator determines that the results are required prior to treatment initiation (eg, clinically significant abnormal laboratory test results requiring follow-up). Analysis of samples can be completed at a local, qualified laboratory. The investigative site should notify the study team if the local laboratory cannot test all the analytes listed in Table 5. If the total thyroxine (Total T4), free T4, uric acid, gamma glutamyl transferase, inorganic phosphorous, very low-density lipoprotein, or globulin parameters are not available through the local laboratory, and alternative arrangements cannot be made, testing of these analytes may be omitted provided other subject- assessments of thyroid function (ie, thyroid-stimulating hormone), lipid metabolism (ie, triglycerides, low-density lipoprotein, high-density lipoprotein, and total cholesterol), and protein metabolism (ie, total protein and albumin) are available and confirmed to be stable as per the Investigator. Alternative arrangements to test the listed analytes are to be made if the Investigator, Medical Monitor, or sponsor determines that they have the potential to impact subject safety. In the event the local laboratory is unable to test any other analytes, they may be omitted in exceptional circumstances after consultation with the sponsor. Such exceptions will not be applied to any of the key safety analytes (see Section 7.2.6).
  - 5 Subjects with normal or non-clinically significant abnormal safety laboratory results observed within 1 month of flare-up-based treatment will not need to have laboratory tests performed at Flare-up Cycle Safety Day 1. The Investigator will determine whether subjects with clinically significant abnormal laboratory results in the most recent assessment will need to be re-assessed prior to beginning flare-up-based treatment. The only exception is for pregnancy testing, which must be performed at the start of each Flare-up Cycle and every 4 weeks thereafter until the end of the cycle. However, if a pregnancy test was performed within 4 weeks prior to the start of treatment for a flare-up or traumatic event, treatment will not be delayed pending repeat pregnancy testing.
  - 6 If urinalysis results are abnormal, then a microscopic evaluation should be completed.
  - 7 Pregnancy testing will be performed for females of child-bearing potential. A urine pregnancy test will be performed only when a serum pregnancy test is not obtained.
  - 8 A flare-up, or substantial high-risk traumatic event likely to lead to a flare-up, will be treated with a minimum of 4 weeks (28 days) of 20 mg palovarotene once daily followed by 8 weeks (56 days) of 10 mg palovarotene once daily (or weight-based equivalent) for a total of 12 weeks (84 days). If the flare-up has not resolved after 12 weeks, treatment will be extended in 4-week intervals until the flare-up resolves.
  - 9 Should a subject experience an intercurrent flare-up, or other substantial high-risk traumatic event likely to lead to a flare-up, at any time during flare-up-based treatment, the 12-week (84 day) dosing regimen will restart upon confirmation by the Investigator (ie, 4 weeks of 20 mg palovarotene followed by 8 weeks of 10 mg palovarotene [or weight-based equivalent]). This may occur more than once during a Flare-up Cycle.
  - 10 At each contact, flare-up status will be assessed for every flare-up and flare-up end date will be recorded when a flare-up resolves. Flare-up status will also be assessed at Week 12 of the initial flare-up (if only one flare-up) or the last ongoing intercurrent flare-up (if more than one flare-up); if any flare-up is still ongoing, the on-going flare-up(s) will be assessed every 4 weeks until the last flare-up has resolved.
  - 11 Flare-up Day 1 is the first day of treatment for a flare-up/substantial high-risk traumatic event (upon confirmation by the Investigator).
  - 12 Pharmacokinetics of palovarotene dosing will be assessed twice: once during the 20-mg regimen at any time between Study Days 4 to 28, and once during the 10-mg regimen at any time during Study Days 32 to 84, for the first treated flare-up only. If not possible for the first treated flare-up, PK blood samples can be obtained during any subsequent flare-up dosing cycle. Blood samples will be collected at pre-dose and 3, 6, 10, and 24 hours post-dose. Subjects who underwent a PK assessment for flare-up-based treatment under PVO-1A-202 Protocol Amendment 3 will not have flare-up PK assessed again. However, these subjects will require a non-flare-up treatment PK assessed at a 3-month safety visit.
  - 13 Flare-up will be evaluated remotely, or by telephone or video-conferencing, unless the Investigator deems that a site visit is necessary. This will include subject-reported current flare-up location, symptoms, and probable causes.

Note: study procedures that require sedation will not be performed.

C-SSRS = Columbia Suicide Severity Rating Scale, PK = pharmacokinetic(s)

**Table 4. Schedule of Assessments for Part D**

Assessment/Procedure	Y1 and Y2 Post Treatment Site Visit 
Informed consent 	X
Knee and hand/wrist radiographs 	X
Linear and knee height growth assessments (<18 years of age) 	X
Physical examination	X
Body weight 	X
Vital signs 	X
Low-dose, WBCT scan (excluding head)	X
Prior/concomitant medications 	At every subject contact
Adverse events 	At every subject contact

 Year 1 (Y1) and Year 2 (Y2) visits following the last dose of study drug will be done within the total study duration from enrolment from Part A. Y1 to be completed in the window of  $\geq 6$  to  $< 18$  months post last dose of study drug. If Part A, B or C EOS date is within the Y1 window then the EOS will serve as the Y1 visit. If Part A, B or C EOS date is prior to Y1 window then Y1 should be scheduled  $\geq 6$  months from Part A, B or C EOS date but still within the Y1 window. Y2 to be completed  $\geq 18 - 24$  months post last dose of study drug. If Part A, B or C EOS date is within the Y2 window then the EOS will serve as the Y2 visit. If Part A, B or C EOS date or Y1 date (if applicable) is prior to Y2 window then Y2 should be scheduled  $\geq 6$  months from the Part A, B or C EOS date or the Y1 date, whichever is later, but still within the Y2 window. If subjects had their last dose of study medication and completed Part A, B or C EOS more than 2 years prior to their consent for Part D, then these subjects will only complete Y2 following their consent for Part D.

 Assessments may be performed remotely (eg, at the subject’s home by qualified study personnel, at a local medical facility, or via videoconference or telephone contact from clinical site personnel) unless the Investigator deems that a site visit is necessary.

 Part D informed consent is required prior to conducting Part D assessments/procedures.

 Subjects found to be skeletally immature will continue knee and hand/wrist radiographs, and linear and knee height measurements (all in triplicate) at Year 1 (Y1) and Year 2 (Y2). Limb/joint AEs in these subjects will be evaluated by any clinical and radiographic assessments deemed appropriate by the Investigator. Once a subject has achieved 100% skeletal maturity (confirmed by radiography and defined by growth plate closures), knee and hand/wrist radiographs will no longer be required, and this will serve as their Part D study completion. In addition, once a subject is 18 years old, linear and knee height growth assessments will no longer be required. If 100% skeletal maturity is not achieved at both locations, then only the location that is still maturing would need to be monitored.

 Knee and hand/wrist radiograph assessments will be conducted at the clinical site unless the Investigator determines they can be performed at a local medical facility. All assessments will be performed at the clinical site if the radiographs cannot be performed locally.

 At each AE assessment, the Investigator must ask the subject about any joint-related complaints.

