**PROTOCOL AMENDMENT 8 SUMMARY OF CHANGES**

This eighth amendment to the protocol for Study PVO-1A-202 was finalized on 30 November 2020.

Location/Section Number	Change	Rationale
Major changes that affected the clinical conduct of the study:		

Protocol Synopsis                      Tables 1 and 4                      Section 1.1.3.2 Clinical Data                      Section 3.1 Overview of Study Design                      Section 3.2 Study Rationale                      Section 7 Study Procedures and Assessments                      Section 2.3 Secondary Objectives                      Section 5.7 Subject Withdrawal or Early Termination                      Section 9.1.10 Follow-up of Adverse Events and Serious Adverse Events
	
Part D was added for skeletally immature subjects who stopped taking study drug for any reason before completion of Part A/B/C. Part D includes yearly visits for up to a 2-year follow-up period following last dose. No dosing will occur during Part D.
 
Assessments obtained in Part D include yearly linear height, knee height, weight, physical exam, vital signs, radiographic assessments of the knee and hand/wrist, low-dose WBCT imaging excluding head, adverse events, and concomitant medications.
 
Participation in Part D will continue as long as subjects remain skeletally immature.
 
The up to 2-year period would begin the last day the subject stopped receiving study drug in Part A/B/C. The total duration of participation in Part C and Part D, is a maximum of 4 years.
 
Secondary objective added for Part D to monitor off treatment longer-term safety in skeletally immature subjects off treatment.
 
Safety will be summarized for Part D.
	
To implement safety measures based on DMC recommendations given the serious identified risk of premature physal closure. Part D is being implemented to ensure that assessments of safety are offered for up to 2 years to subjects who were skeletally immature at the time they stopped taking study drug for any reason before completion of Part A/B/C. A 2-year follow up is an adequate timeframe to assess growth and physal changes off palovarotene treatment. Preliminary data suggest that the risk of premature epiphyseal fusion is higher in subjects with open epiphyseal growth plates who have received the flare-up dosing regimen. A 2-year follow up is an adequate timeframe to assess growth and epiphyseal changes off palovarotene treatment.
 
To allow for provision of study medication until commercial availability.

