As of 04 December 2019, all subjects < 14 years of age were required to interrupt study drug due to a partial clinical hold placed on the palovarotene clinical development program by the US FDA. Treatment will subsequently not be restarted in children <14 years of age.

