#### Study Visits and Assessments

- 1) **For subjects aged under 14 years that are still participating in the study but not currently receiving palovarotene treatment as per the global partial clinical hold or for any other reason**, they will complete Part C EOT/EOS and be invited to participate in Part D and undergo assessments outlined in [Table 4](#).
- 2) **For subjects aged 14 years and older who are being considered for re-starting palovarotene treatment but have NOT yet re-started**, the following minimum assessments are to be done via remote monitoring (video conference/phone calls) by the Investigator (or delegated study staff):
  - a. Chronic visits every 3-6 months (per protocol): assess for childbearing status (females only) and pregnancy prevention measures, CAJIS, ConMeds, adverse events, review subject diary, PROMIS Global Health Scale\*, FOP-PFQ\* (\*assessments that can occur remotely but not required as these are not essential to ensure subjects' safety)
  - b. For females of childbearing status: if pregnancy testing did not continue monthly per protocol post the study drug interruption then at a minimum a self-administered urine pregnancy test is to be done within 4 weeks before re-starting palovarotene treatment.
  - c. All subjects should have laboratory assessments (hematology, biochemistry, urinalysis) within 4 weeks before re-starting palovarotene treatment.
  - d. All subjects who were skeletally immature at the last assessment will have a hand-wrist and knee radiographs within 12 weeks before re-starting palovarotene treatment. For on-treatment subjects who have not reached at least 90% skeletal maturity radiograph assessments should continue per protocol either on site or remotely

Site staff will also assess the subject's ability to restart remotely.

3) **For subjects 14 years and over that plan to reinitiate dosing, once dosing is reinitiated following the required approvals for restart (Ethics Committee and Competent Authority), the following minimum assessments that cannot be performed via remote monitoring must be performed either at the clinical site, at the subject's home (by Symphony nursing) or at a local medical facility in order for the Investigator to adequately monitor the safety of subjects:**

- a. Via remote monitoring (telephone or video conferencing) by Investigator (or delegated study staff):

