**5) End of Treatment/End of Study Assessments:**

- a. The following assessments should be performed via remote monitoring (telephone or video conferencing) by Investigator (or delegated study staff):
  - i. C-SSRS, assess for childbearing status (females only) and pregnancy prevention measures, CAJIS, Con-Meds, adverse events, PROMIS Global Health Scale, FOP PFQ
- b. The following assessments should be performed at the subject’s home (by Symphony nursing) or at a local medical facility: Body weight, vital signs, hematology, biochemistry, urinalysis, pregnancy test (monthly), ConMeds, adverse events, review subject diary

**6) Once on-site visits resume, the following assessments should be performed on site as well as any assessment that was not obtained via remote monitoring or Symphony nurse:**

- a. X-rays, Whole-Body CT, Linear and Knee Height, Physical Exam, ECG.

**7) Informed Consent/Subject Communication:** In consultation with their site IRB/EC, Investigators are required to inform subjects of the temporary changes (during the COVID-19 global pandemic) to the study conduct and monitoring plans that could impact them and their willingness to continue participation in the trial. The method of communication to subjects (e.g., email, phone call, information letter) and documentation of subject/caregiver acknowledgement is to be performed and documented in accordance with local regulations/EC requests and guidance. All contacts with subjects must be filed in the source records.

A risk mitigation assessment will be performed for each subject at the site in order to determine how their participation may be impacted. Sites must ensure that appropriate measures are taken to ensure the safety of FOP subjects in light of the ongoing COVID-19 pandemic, taking into consideration local Ethics Committee and Competent Authority guidance, as well as the ability of individual Investigators and sites to adequately monitor subject safety.

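### Table 4 credits an end-of-study visit as Part D Year 1 or Year 2 by date alone, although the pandemic end-of-study list has no growth-plate, height or CT assessment and the catch-up has no deadline

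*Protocol*

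**What the plan says.** Part D follows skeletally immature subjects off drug for up to two years, with two scheduled visits (Sections 2.3 and 3.1, Table 4). Table 4 is headed as a site visit. Its remote allowance (footnote 2) is attached to consent, weight, vital signs, medications and adverse events. It is not attached to radiographs, heights, physical examination or WBCT.

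Footnote 1 sets the windows: "Y1 to be completed in the window of" 6 to under 18 months after last dose, and Year 2 at 18 to 24 months. It then gives the substitution rules: "If Part A, B or C EOS date is within the Y1 window then the EOS will serve as the Y1 visit", and "If Part A, B or C EOS date is within the Y2 window then the EOS will serve as the Y2 visit".

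Section 3.1 records that, as of 04 December 2019, "all subjects < 14 years of age were required to interrupt study drug". Section 7.7 item 1 says of under-14s still in the study but off drug that "they will complete Part C EOT/EOS and be invited to participate in Part D".

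Section 7.7 item 5 lists the EOT/EOS assessments during the pandemic. The remote part is the C-SSRS, childbearing status and pregnancy prevention, CAJIS, medications, adverse events, PROMIS and FOP-PFQ. The home or local part is "Body weight, vital signs, hematology, biochemistry, urinalysis, pregnancy test (monthly), ConMeds, adverse events, review subject diary". Item 6 adds, for when on-site visits resume: "X-rays, Whole-Body CT, Linear and Knee Height, Physical Exam, ECG".

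The PVO-1A-204 protocol carries the same rules in its Table 4 and Section 7.7.

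**The concern.** Part D was added because of the serious identified risk of premature growth-plate closure (Section 3.2). Section 1.1.3.2 says the effect on growth is likely to be greatest in the youngest, most immature subjects. Radiographs, heights and WBCT are the measurements that address that risk.

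The substitution rule looks only at the calendar. Section 7.7 creates a kind of EOS that leaves those measurements out and sends the under-14s to it. A visit can then be logged as Year 1 when its key content does not yet exist. Because the visit counts as done, nothing in Table 4 marks the content as overdue. In the analysis it would look like a completed assessment with missing values, or be filled by images taken outside the window under a Year 1 label.

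Section 7.7 is also uneven within itself. Item 4b limits postponement of radiographs to subjects at 90% skeletal maturity or more, and the reason in item 4c for postponing heights concerns subjects aged 14 and older. Item 5 lists neither assessment for anyone at EOT/EOS.

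**Working it through.** The plan states no figure to reproduce. Two checks apply: the calendar, and the content of the lists.

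**Calendar.** Inputs: the hold on 04 December 2019 (Section 3.1), the Table 4 windows, and the amendment dates. For PVO-1A-202 the summary of changes reads: "This eighth amendment to the protocol for Study PVO-1A-202 was finalized on 30 November 2020". For PVO-1A-204, Amendment 6 is dated 18 December 2020. Assumption: last dose on the hold date; a child who stopped earlier has earlier windows. Months are days / 30.4375.

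- Year 1 opens: 04 Dec 2019 + 6 months = 04 Jun 2020.
- Year 1 closes and Year 2 opens: + 18 months = 04 Jun 2021.
- Year 2 closes: + 24 months = 04 Dec 2021.
- Hold to Amendment 8: 362 days = 11.9 months. Left of Year 1: 186 days = 6.1 months.
- Hold to PVO-1A-204 Amendment 6: 380 days = 12.5 months. Left of Year 1: 168 days = 5.5 months.

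An EOS held in those remaining months is credited as Year 1. One held from 04 June to 04 December 2021 is credited as Year 2.

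**Content.** Table 4 has 8 rows apart from consent.

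| Table 4 row | In Section 7.7 item 5 | In item 6 |
|---|---|---|
| Knee and hand/wrist radiographs | no | yes |
| Linear and knee height | no | yes |
| Physical examination | no | yes |
| WBCT | no | yes |
| Body weight | yes | – |
| Vital signs | yes | – |
| Medications | yes | – |
| Adverse events | yes | – |

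Item 5 alone covers 4 of 8. Items 5 and 6 together cover 8 of 8. The plan therefore delays the four missing assessments; it does not delete them.

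**Putting the two together.** Item 6 is triggered by the resumption of on-site visits, which Section 7.7 says may differ by country and site. It names no date and does not mention Year 1 or Year 2. Take a remote EOS in the first half of 2021, before 04 June. Footnote 1 counts it as Year 1. The next visit Table 4 schedules is Year 2, at least 6 months later and at 18 to 24 months after last dose. If on-site visits resume only after 04 June 2021, the catch-up images fall in the Year 2 window, leaving one off-drug bone time point where two were planned. If the credited visit is Year 2, Table 4 schedules no later visit to prompt the catch-up.

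Section 7.7 item 2d does not close the gap. It concerns subjects aged 14 and older being considered for restart, and on-treatment subjects below 90% maturity. Off-drug under-14s are neither.

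**The case against.** The strongest reply is that, read as a whole, the protocol still requires these data. Item 6 stands directly below item 5 and names every assessment that item 5 lacks. Sections 7.2.2, 7.2.3, 7.3.2 and 7.4.1 each require their assessment at Year 1 and Year 2, item 1 sends the children to the Table 4 assessments, and Table 4 is a site visit. On this reading item 5 says only what can be done at a distance, and its tension with items 4b and 4c is one of timing. This largely stands. A reader might infer that a credited Year 1 necessarily has no growth-plate data; the documents do not support that. They show a missing deadline and a missing condition. The reply does not supply either, because footnote 1 itself declares the visit served.

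A reader might also infer that, with EOT, EOS and Year 1 merged, no reference remains for measuring off-drug change. That does not hold. Radiographs and heights were scheduled every 6 months on drug for open growth plates (Table 1 footnote 6, Sections 7.2.3 and 7.3.2), and Section 5.7 asks for continued assessment after discontinuation.

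Finally, a new condition cannot make a closed site open. That is true. But an unmet Year 1 would then be recorded as outstanding and not as complete, and Table 4 footnote 5 already allows radiographs at a local facility.

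**Conclusion.** The point holds as a gap in the crediting rule. Footnote 1 counts an EOS as Year 1 or Year 2 on its date alone, while item 5 defines an EOS without 4 of Table 4's 8 non-consent assessments and item 6 defers those 4 without a limit. For a skeletally immature child last dosed on 04 December 2019, a remote EOS before 04 June 2021 can be counted as Year 1 with its growth-plate data collected after the window, or not at all if the child does not return. At worst, one of two planned off-drug bone time points is lost for that child.

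The number affected cannot be determined. It is tempting to conclude from the dates that essentially every child stopped at the hold is caught. That would need assumptions on how quickly sites approved the amendment, that each EOS was remote, and that no on-site visit took place before 04 June 2021. The documents settle none of these, and an ordinary annual EOS under Table 1 includes the imaging and heights.

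The change is worth making because it is cheap and protects the purpose of Part D. It does not bear on the primary efficacy comparison.

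**What to change.** In Table 4 footnote 1 of both protocols, state that a Part A, B or C EOS serves as Year 1 or Year 2 only if the Table 4 radiographs, linear and knee height and WBCT were obtained within that window, with local radiographs accepted as footnote 5 already allows. Otherwise the visit already scheduled remains due.

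Reconcile Section 7.7 items 4, 5 and 6 for subjects with open growth plates, so that the EOT/EOS list, the limits on postponement and the catch-up agree and the catch-up refers to the Year 1 and Year 2 windows. Which clinical rule should prevail is for the sponsor and the Data Monitoring Committee.

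The cost is wording in two protocols. No new procedure is added; some children would need the on-site visit that Table 4 already schedules.
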